## **4.3 Description of Study Procedures**

### **4.3.1 Efficacy**

#### **4.3.1.1 Crohn's Disease Activity Index**

The CDAI is a composite index with weighted domains that quantifies the global disease severity in a single numerical score. It is the oldest and most widely used of several multi-item instruments that have been developed and is validated for use in clinical studies to measure disease activity in CD (Best et al, 1976; Sands and Ooi, 2005). The CDAI measures the severity of active disease using symptom scores that are monitored over the previous week and includes subject-reported symptoms, physician-assessed signs, and laboratory markers. The CDAI score is calculated by summing weighted scores for subjective items (number of liquid or very soft stools, abdominal pain and general well-being) recorded by a diary during a 1-week period, and objective items (associated symptoms, taking antidiarrheal agents such as loperamide/opiates, abdominal mass, hematocrit, daily morning temperature,

and body weight). The CDAI scores range from 0 to 600, with higher scores indicating greater disease activity. Subjects with scores of < 150, 150 to 219, and 220 to 450 represent remission, mild disease, and moderate to severe disease, respectively; whereas subjects with scores of > 450 have very severe disease (Buxton et al, 2007). The CDAI will be calculated at the site in order to determine the eligibility for the study.

The CDAI assessments will be performed at each study visit starting with Visit 2.

[REDACTED]

[REDACTED]

[REDACTED]

[REDACTED]

[REDACTED]

[REDACTED]

[REDACTED]

[REDACTED]

[REDACTED]

[REDACTED]

[REDACTED]

[REDACTED]

[REDACTED]

[REDACTED]	[REDACTED]	[REDACTED]	[REDACTED]	[REDACTED]
[REDACTED]	[REDACTED]	[REDACTED]	[REDACTED]	[REDACTED]
[REDACTED]	[REDACTED]	[REDACTED]	[REDACTED]	[REDACTED]
[REDACTED]	[REDACTED]	[REDACTED]	[REDACTED]	[REDACTED]
[REDACTED]	[REDACTED]	[REDACTED]	[REDACTED]	[REDACTED]

[REDACTED]

[REDACTED]

[REDACTED]

[REDACTED]	[REDACTED]	[REDACTED]	[REDACTED]	[REDACTED]	[REDACTED]	[REDACTED]
[REDACTED]	[REDACTED]	[REDACTED]	[REDACTED]	[REDACTED]	[REDACTED]	[REDACTED]
[REDACTED]	[REDACTED]	[REDACTED]	[REDACTED]	[REDACTED]	[REDACTED]	[REDACTED]
[REDACTED]	[REDACTED]	[REDACTED]	[REDACTED]	[REDACTED]	[REDACTED]	[REDACTED]
[REDACTED]	[REDACTED]	[REDACTED]	[REDACTED]	[REDACTED]	[REDACTED]	[REDACTED]
[REDACTED]	[REDACTED]	[REDACTED]	[REDACTED]	[REDACTED]	[REDACTED]	[REDACTED]

[REDACTED]

[REDACTED]

[REDACTED]

[REDACTED]

[REDACTED]

[REDACTED]

[REDACTED]

[REDACTED]

[REDACTED]

[REDACTED]

[REDACTED]

[REDACTED]

[REDACTED]

[REDACTED]

[REDACTED]

[REDACTED]

[REDACTED]

[REDACTED]

[REDACTED]

[REDACTED]

[REDACTED]

[REDACTED]

[REDACTED]

[REDACTED]

### **4.3.3 Medical History, Physical Examination, Vital Signs, and Electrocardiogram**

#### **4.3.3.1 Medical, Surgical, and Crohn's Disease History**

A complete medical and surgical history will be performed at screening and will include CD history, and current medical conditions, past or present cardiovascular disorders, respiratory, GI, renal, hepatic, neurological, endocrine, lymphatic, hematologic, immunologic, dermatological, psychiatric, genitourinary, and drug history or any other diseases or disorders. Smoking history and alcohol consumption will also be collected.

#### **4.3.3.2 Chest X-ray**

Subjects with a positive PPD test, or an indeterminate QuantiFERON-TB test, or subjects with a history of using anti-TNF $\alpha$  agents for a treatment course of 1 year or longer, who have discontinued an anti-TNF $\alpha$  agent within 6 months prior to screening, must obtain a subsequent chest x-ray that shows no evidence of active TB. If required, a chest x-ray will be completed during the screening period. The chest x-ray may be substituted with documentation of a previous chest x-ray performed within 1 month prior to the first dose of investigational product according to the inclusion criteria.

#### **4.3.3.3 Physical and Neurological Examinations**

Physical examinations will be performed by a physician, physicians' assistant, or certified nurse practitioner, and will include examination of the following: general appearance, head, ears, eyes, nose, throat, neck, skin, cardiovascular system, respiratory system, abdominal system, and basic neurological examination. The subject's weight (each study visit) will be recorded in kg with one decimal place, and height (Screening visit only) will be recorded in cm. If converting from inches, height will be recorded to one decimal place. Measurements should be done with light clothing and no shoes. Complete physical examinations will be

performed according to the Schedule of Study Procedures in [REDACTED]  
[REDACTED]

Demographic characteristics such as sex, race, and ethnicity will also be collected.

#### **4.3.3.4 Visual Acuity Tests and Ophthalmoscopy Examination**

The visual acuity test and ophthalmoscopic examination should be performed according to the Schedule of Study Procedures in [REDACTED]. The visual acuity test will be used to determine the smallest letters a person can read on a standardized chart (eg, Snellen chart or other suitable chart) or a card held 4 to 6 meters (14 to 20 feet) away. The test should be done in a health care provider's office or other suitable environment. The subject will be asked to stand or sit approximately 6 meters (20 feet) from the eye chart with both eyes open. One eye should be gently covered while the subject reads out loud the smallest line of letters they can see on the chart. Best corrected visual acuity (use of corrective refractive lenses is permitted) should be recorded.

The ophthalmoscopic examination should include visually magnified inspection of the internal eye structures and also assessment of the quality of the eye's red reflex after the pupil has been dilated. The appearance of the optic disc and retinal vasculature should be examined and any anomalies in the appearance of the internal ocular structures should be recorded. The presence or absence of cataracts should be noted.

#### **4.3.3.5 Vital Signs**

Vital signs (blood pressure, temperature, pulse rate, and respiration rate) will be obtained at all study visits after the subject has been resting for at least 5 minutes. Subjects are instructed to avoid any hot or cold drinks for 30 minutes if an oral temperature assessment is performed.

[REDACTED]

[REDACTED]

[REDACTED]

[REDACTED]

[REDACTED]

[REDACTED]

[REDACTED]

[REDACTED]

[REDACTED]

### Injection-Site Reactions

The site of injection will be assessed at every visit at which there is an SC injection through the end of the open-label period. Injection-site reactions will be recorded as AEs according to the criteria described in Section 5.4.

[REDACTED]

[REDACTED]

[REDACTED]

[REDACTED]

[REDACTED]

[REDACTED]

[REDACTED]

[REDACTED]

[REDACTED]

[REDACTED]

[REDACTED]

[REDACTED]

[REDACTED]

[REDACTED]

[REDACTED]

[REDACTED]

[REDACTED]

**Pregnancy Test (females of childbearing potential only)**

- Urine human chorionic gonadotropin (hCG)
- Serum beta-hCG (at screening only)

[REDACTED]

[REDACTED]

[REDACTED]

Specific procedures for sample collection, processing, storage, and shipment can be found in a separate Laboratory Manual provided to the sites.

#### **4.3.6 Immunogenicity Evaluation**

Serum samples to measure the presence of ADAs against MEDI2070 will be collected prior to administration of investigational product [REDACTED]

Instructions for sample collection, processing, storage, and shipment can be found in a separate Laboratory Manual provided to the sites.

#### **4.3.7 Biomarker Evaluation and Methods**

Blood and stool samples will be collected and analyzed to evaluate protein, nucleic acid, and cellular biomarkers that relate to MEDI2070 treatment. All biomarker analyses will be conducted to generate hypotheses associated with the mechanisms of action of MEDI2070, identify subsets of subjects responsive to MEDI2070, and to characterize a gene signature.

Specific procedures for sample collection, processing, storage, and shipment can be found in a separate Laboratory Manual provided to the sites.

##### **4.3.7.1 Blood Biomarker Evaluation**

Whole blood samples will be collected in [REDACTED] for total ribonucleic acid (RNA) sample preparation. RNA may be used in the analyses of transcript expression using both [REDACTED] and stored for future analyses.

A second whole blood sample will be collected to evaluate, but will not be limited to the following cell populations: [REDACTED]

[REDACTED]. Blood serum and plasma samples will be collected for analysis of circulating soluble factors in relation to inflammatory cell activities. Factors to be analyzed may include, but are not limited to: [REDACTED]. Additional assays to evaluate levels of [REDACTED] may be conducted.

[REDACTED]

#### 4.3.7.2 Stool Analysis of Fecal Calprotectin and Microbiome

Stool specimens from whole stools already being collected for quantitative determination of fecal calprotectin levels will be collected to support assessment of changes over time in the composition of the [REDACTED]

[REDACTED]. The clinical sites will collect the specimens from stool delivered to the sites by subjects, for processing, shipping, and subsequent testing. Detailed sample collection instructions and kits for the subjects, and specimen processing and shipping instructions and kits for the sites, will be provided through the central laboratory to support centralized testing for each exploratory objective. Stool specimens associated with any study visit at which an ileocolonoscopy is scheduled should be collected prior to the start of the bowel preparation for the ileocolonoscopy.

[REDACTED]

#### 4.3.8 Pharmacogenomics

An additional optional blood sample collection is scheduled to support exploratory study of the relationships between pharmacodynamics and clinical responses in participants, and [REDACTED] and other pathways implicated in IBD pathogenesis using pharmacogenetic methods including but not limited to [REDACTED]

[REDACTED]

[REDACTED]

[REDACTED] Samples will be collected, labeled, stored, and shipped as detailed in the Laboratory Manual.

[REDACTED]

[REDACTED]

[REDACTED]	[REDACTED]	[REDACTED]
[REDACTED]	[REDACTED]	[REDACTED]
[REDACTED]	[REDACTED]	[REDACTED]
[REDACTED]	[REDACTED]	[REDACTED]
[REDACTED]	[REDACTED]	[REDACTED]
[REDACTED]	[REDACTED]	[REDACTED]
[REDACTED]	[REDACTED]	[REDACTED]
[REDACTED]	[REDACTED]	[REDACTED]
[REDACTED]	[REDACTED]	[REDACTED]
[REDACTED]	[REDACTED]	[REDACTED]
[REDACTED]	[REDACTED]	[REDACTED]
[REDACTED]	[REDACTED]	[REDACTED]
[REDACTED]	[REDACTED]	[REDACTED]
[REDACTED]	[REDACTED]	[REDACTED]
[REDACTED]	[REDACTED]	[REDACTED]
[REDACTED]	[REDACTED]	[REDACTED]
[REDACTED]	[REDACTED]	[REDACTED]
[REDACTED]	[REDACTED]	[REDACTED]
[REDACTED]	[REDACTED]	[REDACTED]
[REDACTED]	[REDACTED]	[REDACTED]
[REDACTED]	[REDACTED]	[REDACTED]

[REDACTED]

#### 4.4 Study Suspension or Termination

The sponsor reserves the right to temporarily suspend or terminate this study at any time. The reasons for temporarily suspending or terminating the study may include but are not limited to the following:

1. The incidence or severity of AEs in this or other studies indicates a potential health hazard to subjects
2. Subject enrollment is unsatisfactory
3. Non-compliance that might significantly jeopardize the validity or integrity of the study
4. Sponsor decision to terminate development

If MedImmune determines that temporary suspension or termination of the study is required, MedImmune will discuss the reasons for taking such action with all participating investigators (or head of the medical institution, where applicable). When feasible, MedImmune will provide advance notice to all participating investigators (or head of the medical institution, where applicable) of the impending action.

If the study is suspended or terminated for safety reasons, MedImmune will promptly inform all investigators, heads of the medical institutions (where applicable), and/or institutions conducting the study. MedImmune will also promptly inform the relevant regulatory authorities of the suspension/termination along with the reasons for such action. Where required by applicable regulations, the investigator or head of the medical institution must inform the Institutional Review Board (IRB)/ Independent Ethics Committee (IEC) promptly and provide the reason(s) for the suspension/termination. If the study is suspended for safety reasons and it is deemed appropriate by the sponsor to resume the study, approval from the relevant regulatory authorities (and IRBs/IECs when applicable) will be obtained prior to resuming the study.

#### 4.5 Investigational Products

[REDACTED]

[REDACTED]

[REDACTED]	[REDACTED]	[REDACTED]
[REDACTED]	[REDACTED]	[REDACTED]
[REDACTED]	[REDACTED]	[REDACTED]

[REDACTED]

[REDACTED]

[REDACTED]

**4.5.1.1 Investigational Product Dose Preparation**

The investigational product manager will select the kit assigned by the IVRS/IWRS to prepare the subject's dose.

[REDACTED]

[REDACTED]

[REDACTED]

[REDACTED]

[REDACTED]

[REDACTED]

[REDACTED]

[REDACTED]

[REDACTED]

[REDACTED]

[REDACTED]

[REDACTED]

[REDACTED]

[REDACTED]

[REDACTED]

[REDACTED]

[REDACTED]

[REDACTED]

[REDACTED]

[REDACTED]

[REDACTED]

[REDACTED]

[REDACTED]

[REDACTED]

[REDACTED]

[REDACTED]

[REDACTED]

[REDACTED]

[REDACTED]	[REDACTED]	[REDACTED]		[REDACTED]		[REDACTED]	[REDACTED]
		[REDACTED]	[REDACTED]	[REDACTED]	[REDACTED]		
[REDACTED]	[REDACTED]	[REDACTED]	[REDACTED]	[REDACTED]	[REDACTED]	[REDACTED]	[REDACTED]
	[REDACTED]	[REDACTED]	[REDACTED]	[REDACTED]	[REDACTED]	[REDACTED]	[REDACTED]
	[REDACTED]	[REDACTED]	[REDACTED]	[REDACTED]	[REDACTED]	[REDACTED]	[REDACTED]
[REDACTED]	[REDACTED]	[REDACTED]	[REDACTED]	[REDACTED]	[REDACTED]	[REDACTED]	[REDACTED]
	[REDACTED]	[REDACTED]	[REDACTED]	[REDACTED]	[REDACTED]	[REDACTED]	[REDACTED]
	[REDACTED]	[REDACTED]	[REDACTED]	[REDACTED]	[REDACTED]	[REDACTED]	[REDACTED]
	[REDACTED]	[REDACTED]	[REDACTED]	[REDACTED]	[REDACTED]	[REDACTED]	[REDACTED]
[REDACTED]	[REDACTED]	[REDACTED]	[REDACTED]	[REDACTED]	[REDACTED]	[REDACTED]	[REDACTED]
	[REDACTED]	[REDACTED]	[REDACTED]	[REDACTED]	[REDACTED]	[REDACTED]	[REDACTED]
	[REDACTED]	[REDACTED]	[REDACTED]	[REDACTED]	[REDACTED]	[REDACTED]	[REDACTED]
	[REDACTED]	[REDACTED]	[REDACTED]	[REDACTED]	[REDACTED]	[REDACTED]	[REDACTED]
[REDACTED]	[REDACTED]	[REDACTED]	[REDACTED]	[REDACTED]	[REDACTED]	[REDACTED]	[REDACTED]
	[REDACTED]	[REDACTED]	[REDACTED]	[REDACTED]	[REDACTED]	[REDACTED]	[REDACTED]
	[REDACTED]	[REDACTED]	[REDACTED]	[REDACTED]	[REDACTED]	[REDACTED]	[REDACTED]
	[REDACTED]	[REDACTED]	[REDACTED]	[REDACTED]	[REDACTED]	[REDACTED]	[REDACTED]

[REDACTED]		[REDACTED]						
[REDACTED]	[REDACTED]	[REDACTED]	[REDACTED]	[REDACTED]	[REDACTED]	[REDACTED]	[REDACTED]	
[REDACTED]	[REDACTED]	[REDACTED]	[REDACTED]	[REDACTED]	[REDACTED]	[REDACTED]	[REDACTED]	
	[REDACTED]	[REDACTED]	[REDACTED]	[REDACTED]	[REDACTED]	[REDACTED]	[REDACTED]	
	[REDACTED]	[REDACTED]	[REDACTED]	[REDACTED]	[REDACTED]	[REDACTED]	[REDACTED]	

IV = intravenous; OL = open-label; SC = subcutaneous

[REDACTED] [REDACTED]

[REDACTED]

[REDACTED]  
[REDACTED]  
[REDACTED]  
[REDACTED]  
[REDACTED]  
[REDACTED]

[REDACTED]

[REDACTED]  
[REDACTED]  
[REDACTED]  
[REDACTED]  
[REDACTED]  
[REDACTED]  
[REDACTED]  
[REDACTED]

[REDACTED]

[REDACTED]  
[REDACTED]  
[REDACTED]  
[REDACTED]

[Redacted text block]

[Redacted text block]

[Redacted text block]

[Redacted text block]

[Redacted text block]

[Redacted text block]

[Redacted text block]

[Redacted text block]

[REDACTED]

[REDACTED]

[REDACTED]

[REDACTED]

## Infections

If according to the investigator a subject shows signs of a clinically significant infection during the double-blind, placebo-controlled period, the subject will be withdrawn from the study. A clinically significant infection will be defined as:

- An infection that meets criteria for a TESAE
- An infection that is Grade 3 or higher severity
- A mycobacterial infection
- A systemic fungal infection
- A viral infection requiring parenteral antiviral therapy

- A bacterial infection requiring IV antibiotics

During the open-label period, MEDI2070 should not be administered to a subject with a clinically significant active infection treated with oral or IV antimicrobials, antivirals, or antifungals until it is confirmed by the investigator that the infection has resolved.

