#### **4.1.5 Withdrawal from the Study**

Subjects are at any time free to withdraw from the study (investigational product and assessments), without prejudice to further treatment (withdrawal of consent). Such subjects will always be asked about the reason(s) and the presence of any AEs. If possible, they will be seen and assessed by an investigator and every attempt will be made to complete the early termination visit assessments (see Early Termination Visit and Safety Follow-up Period, Section 4.2.3). AEs will be followed up. If a subject withdraws from further participation in the study, then no further study visits or data collection should take place.

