#### **4.1.6 Discontinuation of Investigational Product**

An individual subject will not receive any further investigational product if any of the following occur in the subject in question:

1. Withdrawal of consent from further treatment with investigational product or lost to follow-up
2. An AE that, in the opinion of the investigator or the sponsor, contraindicates further dosing
3. Subject has had, or requires intra-abdominal surgery
4. Pregnancy (see Section 5.6.4) or intention to become pregnant
5. Subject receives any live vaccine
6. Severe noncompliance to this study protocol, as determined by the investigator or medical monitor
7. Recurrence of significant CD symptoms, that warrants escalation in therapy, according to investigator judgment, at any time during the study
8. Subject develops a malignant neoplasm
9. Mycobacterial infections, systemic fungal infections, or viral infections requiring hospitalization or parenteral antiviral therapy
10. Failure to receive a scheduled dose of investigational product within the dosing window during the double-blind periods of the study (Section 3.1.2)
11. Failure to receive 2 consecutive scheduled doses of investigational product within the dosing window during the open-label period of the study (Section 3.1.2)

Subjects who are permanently discontinued from further receipt of investigational product, regardless of the reason (withdrawal of consent, due to an AE, other), will be identified as

having permanently discontinued treatment. Subjects who permanently discontinue treatment may either be considered to have completed the study or not to have completed the study.

Subjects who are permanently discontinued from receiving investigational product will be followed for safety for 28 weeks after the last dose of investigational product, including the collection of any protocol specified blood, urine, or fecal specimens, unless consent is withdrawn or the subject is lost to follow-up or enrolled in another clinical study. In addition, subjects who are permanently discontinued from further receipt of investigational product will be referred for appropriate medical care by the investigator, as required. Such referral will be taken in coordination with the subjects' personal physician.

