## **4.6.3 Methods for Unblinding**

### **4.6.3.1 Unblinding in the Event of a Medical Emergency**

In the event of a medical emergency, the investigator may unblind an individual subject's investigational product allocation. Instructions for unblinding an individual subject's investigational product allocation are contained in the IVRS/IWRS manual. In general, unblinding should only occur if management of the medical emergency would be different based on the subject having received investigational product. In the majority of cases, the management of a medical emergency would be the same whether or not investigational product was received by the subject. If this was the case, the investigational product allocation should not be unblinded.

MedImmune retains the right to unblind the treatment allocation for TESAEs that are unexpected and are suspected to be causally related to an investigational product and that potentially require expedited reporting to regulatory authorities.

If a subject's investigational product allocation is unblinded prior to that subject having completed the Week 28 visit and all its associated assessments, the subject should be discontinued from investigational product.

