In the event that the dose of any of the medications listed above must be reduced for the subject's safety, investigational product must be withdrawn and an early termination visit must be completed.

Background CD medication is not regarded as investigational product, and will not be provided by the sponsor.

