#### **4.7.2 Prohibited Concomitant Medications**

Subjects must be instructed not to take any medications, including over-the-counter products, without first consulting with the investigator.

The following medications or interventions are considered exclusionary and are not permitted as specified below through Week 52 of the study. The sponsor must be notified if a subject receives any of these during the study:

- Natalizumab (Tysabri®)
- Anti-TNF $\alpha$  agents
- Vedolizumab
- Any commercially available or experimental biologic agent, eg, ustekinumab
- Calcineurin inhibitors eg, cyclosporine (Neoral®) and tacrolimus (FK 506/Prograf®)
- Mycophenolate mofetil (CellCept®)
- Sirolimus (rapamycin)
- IV or intramuscular steroids
- Topical (rectal) aminosalicylic acid (eg, mesalamine) or topical (rectal) steroids
- Thalidomide
- Live attenuated vaccine
- Intra-abdominal surgery
- Elemental diet
- Any experimental product or device as specified in Section 4.1.3 (exclusion criterion #31)

In the event that a subject receives a treatment/intervention listed above, investigational product must be withdrawn and an Early Termination Visit must be completed (see Early Termination visit, Section 4.2.3).

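### The double-blind infection rule directs withdrawal from the study, which is inconsistent with the 28-week safety follow-up that Section 4.1.6 keeps after product is stopped

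*Combined protocol and SAP*

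**What the plan says.** Protocol Section 4.5.1, under the unnumbered heading Infections, covers the double-blind period. If in the investigator's view a subject "shows signs of a clinically significant infection during the double-blind, placebo-controlled period, the subject will be withdrawn from the study". Six categories define a clinically significant infection: one that is a treatment-emergent SAE, one of Grade 3 or higher, mycobacterial, systemic fungal, viral needing parenteral antivirals, and bacterial needing IV antibiotics. In the open-label period the same section only holds dosing until the infection has resolved.

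Section 4.1.6 lists reasons to stop investigational product. Criterion 9 is "Mycobacterial infections, systemic fungal infections, or viral infections requiring hospitalization or parenteral antiviral therapy". Anyone permanently taken off product, whatever the reason, "will be followed for safety for 28 weeks after the last dose of investigational product", including protocol specimens, "unless consent is withdrawn or the subject is lost to follow-up or enrolled in another clinical study". Infection is not among these exceptions.

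The synopsis and Section 3.1.1 promise three safety visits over 28 weeks after the last dose to all subjects. Section 5.6.4.1 (pregnancy) says that dosing stops but that the subject is not withdrawn from the study. Section 5.4.1 collects adverse events until the subject's participation ends.

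For subjects who do not enter the open-label period, both SAPs count treatment-emergent events up to 28 weeks after the last blinded dose (Section 3.8.1.2 of the SAP written after early termination; Section 3.9.1.2 of the full SAP).

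**The concern.** A subject with, say, a mycobacterial infection in the double-blind period falls under two instructions with different stated consequences. Section 4.1.6 stops product and keeps the subject in safety follow-up. The infection rule removes the subject from the study and says nothing about follow-up. A site could reasonably take the second as the end of participation, and under Section 5.4.1 that ends adverse-event collection.

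Infection is the first potential risk named in Section 1.5.1. Clinically significant infections have a planned summary in protocol Section 4.8.5.1, and infections are a category of special interest in Table 3.9.2-1 of the full SAP. The subjects whose later safety data are of most interest for this risk would then be those with an incomplete 28-week window. The index infection would still be recorded. What is at risk is any later event, possibly the outcome of the infection, and the follow-up specimens.

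**Working it through.** The plan gives no figure to reproduce here. The check is a comparison of texts, plus simple arithmetic on the follow-up window.

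**1. Do the two rules cover the same subjects?**

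| Category in the infection rule | Named in 4.1.6 criterion 9? |
|---|---|
| Treatment-emergent SAE | No |
| Grade 3 or higher | No |
| Mycobacterial | Yes |
| Systemic fungal | Yes |
| Viral, parenteral antivirals | Yes |
| Bacterial, IV antibiotics | No |

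Three of the six categories appear in both. For the other three, product also stops once the subject is withdrawn, and the follow-up sentence in Section 4.1.6 applies whatever the reason for stopping. The difference between the two lists is not itself claimed as a defect.

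**2. Are stopping product and leaving the study the same thing here?** No. Section 5.6.4.1 directs the first and rules out the second in one sentence. Section 4.1.6 also says that subjects who stop treatment may or may not count as having completed the study.

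**3. Which text is out of line?** The synopsis and Section 3.1.1 promise follow-up to all subjects. Section 4.1.6 lists three exceptions, none of them infection. The Note to File in the SAP written after early termination (Section 6.3) treats follow-up visits for withdrawn or early-terminated patients as expected; what failed there was device programming. These texts agree with one another, and the infection rule is the one that departs from them.

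**4. How much follow-up could a literal reading lose?**
- Inputs: double-blind doses at Weeks 0, 4, 8, 12, 16, 20 and 24 (Table 3.1.2-1); a follow-up window of 28 weeks from the last dose (Section 4.1.6).
- Assumptions: dosing is on schedule, and participation ends at the infection. The infection then falls 0 to 4 weeks after the last dose.
- Weeks lost = 28 − (weeks since last dose). Lower end: 28 − 4 = 24, and 24/28 = 86%. Upper end: 28 − 0 = 28, or 100%. Up to three safety visits go with them.
- Example: last dose at Week 8, infection at Week 10. The window runs to Week 8 + 28 = Week 36, so 36 − 10 = 26 of the 28 weeks go unrecorded.
- If the site follows Section 4.1.6 instead, 0 weeks are lost.

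**The case against.** The strongest reply is that both rules can be obeyed together. A subject withdrawn for infection has also permanently stopped product, so Section 4.1.6 already applies, and the infection rule never says that follow-up ends. Section 4.2.3, which Section 4.1.5 cites for the early termination visit and safety follow-up, is redacted and may say this outright. The text just before the Infections heading is redacted too. Much of this stands. It makes lost follow-up a risk of misreading rather than a consequence that the protocol sets out. It does not make the wording consistent, since a site must go to another section to learn that the plain words do not mean what they appear to.

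Two stronger readings are tempting, and the documents support neither.

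- A reader might infer from Section 4.1.5 that study withdrawal always ends assessments. That section opens "Subjects are at any time free to withdraw from the study (investigational product and assessments", and later says that visits and data collection cease. But the opening sentence goes on to identify this as withdrawal of consent, so it describes the subject's own decision. No visible text defines what withdrawal directed by the investigator ends.
- A reader might count event rules and present the infection rule as a lone exception, because others stop product (after unblinding, for example, "the subject should be discontinued from investigational product") or add an early termination visit (Sections 4.7.1 and 4.7.2). The tally depends on how rules are grouped, and some of them are dosing holds that do not address what happens to the subject afterwards. It adds nothing to step 3 of the working.

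Section 5.4.2 softens the loss somewhat. The investigator follows unresolved events for as long as medically indicated, and the sponsor may ask for more information. That follow-up is not recorded further in the eCRF, however, and it does not cover new events.

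**Conclusion.** The infection rule is inconsistent with Section 4.1.6 and should be corrected. The point is modest. The loss per affected subject is 0 weeks if the site follows Section 4.1.6, and 24 to 28 of 28 weeks if the site applies the infection rule literally to a subject dosed on schedule. The upper figure is a ceiling, not an expected loss. The documents give no infection rate, so no number of affected subjects can be stated.

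A reader might infer that the sponsor meant to drop follow-up after infection. The visible text points the other way. The conclusion rests on that visible text; Section 4.2.3 could already settle the matter.

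The effect is confined to descriptive safety summaries, because both SAPs plan no statistical comparison of safety data (Section 3.8 of the SAP written after early termination; Section 3.9 of the full SAP). Sample size and power are not affected.

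**What to change.** In the infection rule, replace the direction to withdraw the subject from the study with a direction to discontinue investigational product permanently and keep the subject in the 28-week safety follow-up of Section 4.1.6. A cross-reference from criterion 9 to the six-category list is optional; criterion 9 must still stand for the open-label period.

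In a running trial this would cost one amended sentence and a memo to sites, with no new visits. Here the study was terminated early with 29 subjects randomized, so an amendment can no longer help enrolled subjects. Two steps remain. First, check whether any subject withdrawn for a double-blind infection has less than 28 weeks of recorded follow-up after the last dose, keep those cases apart from truncation caused by study closure, and report any that are found beside the adverse-event tables. Second, correct the sentence before the protocol text is reused.
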